#### 6.4 HANDLING MISSING DATA

Every effort will be made to collect all data points in the study. The sponsor plans to minimize the amount of missing data by appropriate management of the prospective clinical trial, proper screening of study participants, and training of participating investigators, monitors and study coordinators.

A sensitivity analysis will be performed for the primary effectiveness endpoint where a missing 3-month assessment of CSS will be replaced using the following imputations for calculating the improvement in CSS:

- Worst case (highest CSS score observed for all follow-ups available)
- Last observation carried forward (30 day or baseline assessment).
- Best case (lowest CSS score observed for all follow-ups available for a subject)

Imputations will not be made on secondary endpoint data, but all data available will be summarized.

#### 6.5 SECONDARY EFFECTIVENESS ENDPOINTS

Descriptive statistics will be used to summarize the secondary endpoints including mean, standard deviation, median, range for continuous data and frequency and percentage for categories values.

The secondary endpoints will be split into two categories, either Inferential or simply Descriptive. The inferential secondary endpoints will be tested using the hierarchical approach of gatekeeping to ensure the overall alpha for the trial is maintained. Descriptive secondary endpoints will not have any hypothesis testing performed.

In addition to regular annual reports, there are expected to be 3 reports prepared (3-month, 6 month, final – see **Section** Error! Reference source not found.), and the first report will have the 3 month results including the primary endpoint and all inferential secondary endpoints tested. The 6 month and final reports will include 95% confidence intervals for the endpoints that were used in the primary and inferential secondary endpoints for the longer-term visits to provide support for longer-term performance of these same endpoints.

##### 6.5.1 Hierarchical testing

If the primary endpoint passes, a subset of the secondary endpoints (inferential) will have hypothesis tests performed for potential labeling claims. These endpoints will be tested the specific order presented below. If the first secondary endpoints passes the hypothesis test (rejects the null hypothesis), then the next secondary endpoint will be tested. Testing will continue up to the point that a hypothesis test fails. Endpoints that follow will then simply use descriptive statistics and no p-values will be presented. Since this testing relies first on the primary endpoint

passing, the 6-month data will be used instead should 3-month COVID 19 related missed visits reduce the evaluable data to <54.

### 6.5.2 Secondary Endpoint 1 (Inferential) – CSS Responders at 3 months

Endpoint Definition: The CSS score at 3 months. A participant is considered a responder if the 3-month CSS score has improved by at least 1 point from the baseline CSS score.

Hypothesis:

Ho:  $p \leq 60\%$

Ha:  $p > 60\%$ ,

where  $p$ =proportion of responders and 60% is the same performance goal that Cellfina used to achieve approval.

Analysis cohort: The mITT cohort.

Statistical Analyses: The count and proportion of responders will be summarized along with an exact binomial 2-sided 95% confidence interval for the proportion of responders along with a p-value.

Definition of Success: If the lower bound of the 2-sided 95% confidence interval is greater than or equal to 0.6 then we will reject the null hypothesis and declare proportion of responders are greater than 60%.

### 6.5.3 Power calculation: The sample size for this trial is based upon the primary endpoint. With an observed performance of 81% responder in initial pilot data and expected sample size of 54, a one-sided alpha of 0.025 and performance goal of 60%, there will be > 90% power to test this hypothesis. Secondary Endpoint 2 (Inferential) – Improvement in GAIS at 3 months

Endpoint Definition: The GAIS score at 3 months as determined by a blinded and independent evaluator. A participant is considered improved if the GAIS assessment is improved (1), much improved (2) or very much improved (3).

Hypothesis:

Ho:  $p \leq 60\%$

Ha:  $p > 60\%$ ,

where  $p$ =proportion of Improved and 60% is an assumed acceptable performance goal for this endpoint and trial size.

Analysis cohort: The mITT cohort.

Statistical Analyses: The count and proportion of participants with GAIS evaluations of improved will be summarized along with an exact binomial 2-sided 95% confidence interval for the proportion of responders along with a p-value. Additionally, count and proportions will be summarized for each of the 7 categories of GAIS.

Definition of Success: If the lower bound of the 2-sided 95% confidence interval is greater than or equal to 0.6 then we will reject the null hypothesis and declare proportion of responders are greater than 60%.

Power calculation: The sample size for this trial is based upon the primary endpoint. With an observed performance of >95% improved in initial pilot data and expected sample size of 54, a one-sided alpha of 0.025 and performance goal of 60%, there will be > 90% power to test this hypothesis.

Long term success: The change in GAIS and proportion of responders will be summarized at the 12 month visit. The 95% confidence intervals are intended to support long-term performance claims.

#### **6.5.4 Secondary Endpoint 3 (Inferential) – Patient Satisfaction at 3 months**

Endpoint Definition: The patient satisfaction assessment measured at 3 months. Patient satisfaction is collected using an evenly balance scale with 5 categories: very satisfied, satisfied, neither satisfied nor dissatisfied, dissatisfied, very dissatisfied. The general “Satisfied” category is defined as those that indicated they were satisfied or very satisfied with their outcome.

Hypothesis:

Ho:  $p \leq 60\%$

Ha:  $p > 60\%$ ,

where  $p$ =proportion satisfied and 60% is an assumed acceptable performance goal for this endpoint and trial size.

Analysis cohort: The mITT cohort.

Statistical Analyses: The count and proportion of participants satisfied with their outcome will be summarized along with an exact binomial 2-sided 95% confidence interval for the proportion of responders along with a p-value. Additionally, count and proportions will be summarized for each of the 5 levels of patient satisfaction.

Definition of Success: If the lower bound of the 2-sided 95% confidence interval is greater than or equal to 0.6 then we will reject the null hypothesis and declare proportion of responders are greater than 60%.

Power calculation: The sample size for this trial is based upon the primary endpoint. With an observed performance of 67% satisfied in initial pilot data and expected sample size of 54, a one-sided alpha of 0.025 and performance goal of 60%, there will be ~17% power to test this hypothesis, however it is believed performance will be better in this trial.

#### **6.5.5 Secondary Endpoints (Descriptive)**

Descriptive statistics were used to summarize other secondary endpoints including mean, standard deviation, median, range for continuous data and frequency and percentage for categories values.

## 6.6 ADDITIONAL OUTCOME MEASURES

### 6.6.1 Learning Curve Analysis

To explore the potential for possible learning curves, descriptive analyses will be made using sites with at least 5 participants enrolled (including roll-in participants). Note that if more than one investigator should be active at a site, for this analysis each investigator will be treated as a site, but it is not expected.

The following summaries will be prepared in sequentially treated participants across these sites for 1st participant, 2nd participant, 3rd participant, etc.:

- Mean Baseline CSS
- Mean Change in CSS at 3 months
- Proportion of participants with device related AE
- Proportion of participants with serious device related AE

Because multiple procedures may occur on the same day, additional descriptive analyses will summarize these same values for sequentially treated participants across these same sites for 1st procedure date, 2nd procedure date, 3rd procedure date, etc.

## 6.7 EXPLORATORY ANALYSIS

Additional exploratory statistical analysis may be performed including subgroup analyses and participant reported outcomes.

## 6.8 PARTICIPANT ACCOUNTABILITY

The disposition of participants will include the number and percentages of participants for the following categories:

- Participants who enrolled
- Participants who screen failed
- Participants who underwent the deployable hook procedure in the ITT
- Participants who are in the mITT
- Participants who are in the PP

All percentages will be based on the number of subjects who underwent the deployable hook procedure. The primary reason for screen failure and early termination will also be summarized.

The participant accountability for each study follow-up will be presented. The following categories will be included:

- Theoretical number of participants
- Active (not terminated) participants or expected
- Number of participants who completed (at least partially) the visit
- Participants included in effectiveness data
- Participants included in safety data
- Participants who missed a visit
- Participants who terminated prior to the 12-month visit

The reasons for terminating early will be listed, as will the participants and visits that were affected by COVID-19.

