**1 PROTOCOL SYNOPSIS**

Title	Controlled Focal Fibrous Band Release Method
Short Title	CONFIRM
IDE No.	G200312
Study Device	Avéli (formerly Deployable Hook)
Intended Use	The intended use of the subject device is to separate tissue (fibrous septa) and provide transillumination for anatomical navigation.
Proposed Indications for Use	Avéli is indicated for temporary reduction in the appearance of cellulite in the buttocks and thigh areas of adult females as supported by clinical data demonstrating benefits through three months of observation.
Study Design	Single arm, multicenter, open label pivotal study
Study Objective	Demonstrate safety and effectiveness of the deployable hook in reducing the appearance of cellulite
Study Duration	1-year participant follow-up
Number of Sites	7 sites in United States and 2 sites in Australia
Enrollment	74 participants, including 6 roll-in patients
Primary Effectiveness Endpoint	Mean change (improvement) from baseline in the Cellulite Severity Scale (CSS)  is $\geq 1$ point at 3 months.
Primary Safety Measure	Absence of device related Serious Adverse Events (SAEs) directly attributable to the device at 30 days.

---

 CSS = CSS-A (Number of Evident Depressions) + CSS-B (Average Depth of Depressions) – 1

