## 6 STATISTICAL METHODS

### 6.1 STATISTICAL AND ANALYTICAL PLANS

#### 6.1.1 Analysis Cohorts

- **Modified Intent-to-Treat (mITT) Cohort:**

The modified intent-to-treat mITT data set will include all enrolled participants that underwent the DH procedure but exclude any roll-in participants. The mITT analysis cohort will be used for all described analyses.

- **Per Protocol (PP) Cohort:**

The PP cohort will be used as a secondary support of the primary effectiveness m-ITT analysis and may be used in exploratory analysis.

The PP analysis set will exclude participants with the following significant protocol deviations:

- 1) Participants with significant violations of the inclusion and exclusion criteria, including:
  - Mild cellulite
  - Impactful co-morbidity outlined in eligibility criteria
  - BMI >30.1
  - Pregnancy or weight gain/loss >10% of baseline weight
- 2) Participants who do not have images for primary effectiveness endpoint (missed, COVID-19, etc.)

Overall, protocol deviations for active participants will be summarized by severity (major/minor), type by visit, and by site. Any deviations or issues reported to IRB/HREC and will be described.

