#### Hypothesis:

- $H_0: D < 1$
- $H_a: D \geq 1,$

where  $D$  = improvement in the CSS score from baseline to 3 months, and 1 is the performance goal.

The endpoint with a sample size of 54 participants will be adequately powered with at least 90% power to test the hypothesis that the mean reduction at 3-months is equal to or greater than 1. This study's sample size will be increased by 25% for a total N of 68 to account for the potential of missed visits amid the pandemic.

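### Section 6.8 divides every disposition row by the number treated, so the screen-failed percentage is a ratio to treated participants and not a screen-failure proportion

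*Combined protocol and SAP*

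**What the plan says.** Section 6.8 introduces its disposition table with "The disposition of participants will include the number and percentages of participants for the following categories". Five rows follow:

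- "Participants who enrolled"
- "Participants who screen failed"
- "Participants who underwent the deployable hook procedure in the ITT"
- the mITT cohort
- the PP cohort

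The sentence after the list fixes one base for all of them: "All percentages will be based on the number of subjects who underwent the deployable hook procedure". No row is exempted, and the section names no second denominator such as screened, consented or enrolled. It also promises a summary of the primary reasons for screen failure and early termination.

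Section 6.1.1 treats enrollment and treatment as two separate conditions. The mITT set "will include all enrolled participants that underwent the DH procedure", less the roll-ins. The ITT set adds the roll-ins back.

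**The concern.** A percentage in a disposition table is normally read as the share of a group that falls in a category. That requires the people counted in the row to belong to the group in the denominator. A woman who fails screening never has the procedure, so she is in the numerator of the screen-failed row and cannot be in its base. For the enrolled row the relation is reversed: the base is contained in the row, so the percentage can never be below 100%.

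Untreated participants are foreseeable here. The schedule of events (Table 1) checks eligibility at screening and again before the procedure on Day 0, when the pregnancy test and vitals are also done. One exclusion criterion concerns infection or fever on the day of the procedure itself.

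The trial is single-arm and judged against fixed performance goals. A reader will therefore use the disposition table, among other things, to see how selected the treated cohort is. A screen-failure figure on the wrong base overstates the share screened out for anyone who takes it at face value.

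**Working it through.** Section 6.8 states no number to reproduce, so the check compares each row with its base and then works through illustrative counts.

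**Inputs.**
- Planned enrollment, from the synopsis: "74 participants, including 6 roll-in patients".
- Planned number without roll-ins, from section 6.3.7: "sample size will be increased by 25% for a total N of 68". The two agree: 54 × 1.25 = 67.5, rounded up to 68, and 68 + 6 = 74.
- Number treated, T: taken as 74. This is an assumption (every planned participant is treated).
- Screen failures, S, and enrolled but untreated, u: not given in the documents. Ranges are assumed below.

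**Row against base, under the rule as written (base = T).**

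| Row | Is the row contained in the treated group? | Percentage |
|---|---|---|
| Enrolled | No; it contains the treated group | (T + u)/T, never below 100% |
| Screen failed | No; the two do not overlap | S/T, no upper limit |
| Treated (ITT) | Yes; it is the treated group | T/T = 100% |
| mITT | Yes | 68/74 = 91.9% as planned |
| PP | Yes | at most 100% |

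**Screen-failed row.** The rule gives S/T. If nobody else goes untreated, the number screened is S + T and the proportion is S/(S + T). The rule's figure is larger by the factor (S/T) ÷ [S/(S + T)] = 1 + S/T.

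| S (assumed) | Rule: S/74 | Of those screened: S/(S + 74) |
|---|---|---|
| 10 | 13.5% | 10/84 = 11.9% |
| 20 | 27.0% | 20/94 = 21.3% |
| 40 | 54.1% | 40/114 = 35.1% |
| 74 | 100.0% | 74/148 = 50.0% |
| 80 | 108.1% | 80/154 = 51.9% |
| 100 | 135.1% | 100/174 = 57.5% |

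The figure is on the wrong base for every S of at least 1. It passes 100% only when S is greater than T, which under these assumptions means that more than half of those screened fail.

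**Enrolled row.** With T = 74:
- u = 0: 74/74 = 100.0%
- u = 2: 76/74 = 102.7%
- u = 5: 79/74 = 106.8%
- u = 10: 84/74 = 113.5%

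If every enrolled participant is treated, the row is exactly 100% and nothing is wrong with it. Whether u can be above zero depends on when a participant counts as enrolled, which section 6.8 does not say.

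**The case against.** The strongest reply is that little depends on this sentence. Section 6.8 prints counts beside the percentages, so anyone can form the correct rate from the same table. The plan never promises a quantity called a screen-failure rate, and a ratio to treated participants is openly labelled once its base is stated. Screen-failure reasons are tabulated, and the eligibility criteria and the demographic and medical history summaries (section 6.9) also show how the cohort was selected. The screen-failure counts used above are assumed. The document is headed as an abbreviated protocol with some broken cross-references, so a definition of enrollment may exist elsewhere.

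Most of that stands, and it limits the point. It does not rescue the sentence, which covers every row without exception and gives the screen-failed row a base that excludes the people it counts.

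A reader might infer more than the text supports:

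- *That three of the five rows are wrong.* Only the screen-failed row is improper in every case. The enrolled row is affected only if someone enrolled goes untreated. The treated row at 100% is correct, because it is the base.
- *That the rule hides loss between enrollment and treatment.* The counts of enrolled and treated are both printed, and an enrolled figure above 100% would draw attention to the gap.
- *That the table will show figures above 100%.* This depends on counts that the documents do not give.
- *That this percentage is the main evidence on selection.* The other summaries just listed bear on the same question.

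**Conclusion.** The point holds as a minor error in a descriptive table. As written, the screen-failed percentage is a ratio to treated participants and will be too high if read as a proportion of those screened. With 74 treated and no other untreated participants, the excess is 27.0% against 21.3% at 20 failures, and 54.1% against 35.1% at 40. Both failure counts and the 74 are assumptions. The direction of the error does not depend on them.

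The enrolled row is a conditional problem that cannot be settled from the text supplied, because the point of enrollment is not stated in section 6.8. The treated, mITT and PP rows need no correction of arithmetic. The primary and secondary endpoints, the safety analysis, the sample size, power and alpha do not use this table and are unaffected.

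**What to change.** First state the point of enrollment (for example, consent, confirmed eligibility or start of the procedure), and whether a screen failure can also count as enrolled. Then replace the single-denominator sentence with one that gives the base by row:

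*Percentages for the enrolled and screen-failed rows are based on all consented/screened participants; the percentage treated (ITT) is based on enrolled participants; percentages for the mITT and PP cohorts are based on treated participants.*

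The definition has to come first. If enrollment means signing consent, the enrolled row on a consented base is 100% by construction, and the treated-of-enrolled row carries the information. If enrollment comes later, both rows are informative. Moving the treated row to an enrolled base also makes it show any loss before the procedure, which a fixed 100% cannot.

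The cost is a short edit to section 6.8 and changed denominators in one table program. No new data are needed beyond the counts that the section already requires and the number consented/screened.

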## 6.9 OTHER STUDY SUMMARIES

- Protocol Deviations
  - Minor and major deviations will be summarized together and separately
- The following will be tabulated with appropriate summary statistics:
  - Demographics/Ethnicity
  - Medical History
  - Procedural Data

## 6.10 DATA COLLECTION AND ELECTRONIC CASE REPORT FORM (eCRF) COMPLETION

The Investigator, or designee, will enter data from the clinic's medical records and study source worksheets into an online electronic data capture (EDC) system. The data will remain secure as study personnel will be trained to use a password protected login. Sponsor designated monitors will perform clinical monitoring, including verification of eCRFs and the source documentation.

Data entry should occur in a timely manner for accuracy, but, especially for complying with regulations if unanticipated or serious adverse event occurs (within 24 hours). If significant delays in entry occur frequently, formal corrective plan will be established.

## 7 INVESTIGATOR RESPONSIBILITIES

### 7.1 INVESTIGATOR FILES

For the study duration the Investigator will:

- maintain complete and accurate documentation, including but not limited to, medical records, study progress records, laboratory reports, CRFs,
- signed and dated informed consent forms,
- all correspondence with the IRB/HREC,
- Sponsor personnel/representatives, and other regulatory agencies,
- the protocol, and
- documentation for each deviation from the protocol,
- records of receipt, use, or disposition of each device,
- record of the exposure to the study device,
- adverse event records,
- information regarding participant discontinuation or completion of the study,
- any other supporting data, and
- any other records that FDA or local regulation requires to be maintained

**Abbreviated CONFIRM Protocol****7.2 INSTITUTIONAL REVIEW BOARD PROTOCOL/ HUMAN RESEARCH ETHICS COMMITTEE AND INFORMED CONSENT APPROVALS**

The ICFs that are used should be in accordance with the current guidelines as outlined by local regulations (i.e. 21CFR Part 50, Good Clinical Practices (GCP) guidelines and ISO 14155).

The Investigator must have a written approval from the IRB/HREC prior to recruiting participants in the study. Any materials used for recruitment, as well as any other participant facing materials such as questionnaires, must also be approved by IRB/HREC. A copy of the written approval must be provided to the study sponsor and should include the following.

- A statement of IRB/HREC approval for the proposed study at the institution
- The date the study was approved
- A statement that the informed consent document (version date referenced) has been approved (may be a separate documented letter)
- A listing of any conditions or requirements attached to the approval imposed by the IRB/HREC
- Identification of the approved Principal Investigator
- The signature of the IRB/HREC chairperson

If the Investigator or Sub-Investigator is a member of the IRB/HREC, the letter should state that he/she did not participate in the review or approval of the protocol or informed consent (may be provided under a separate letter).

Until the study is completed, the Investigator will advise their IRB/HREC of the study progress, minimally, on an annual basis. Written approval must be obtained yearly to continue the study. Any amendments to the protocol, as well as associated consent form changes and participant facing materials, will be submitted to the IRB/HREC and written approval obtained prior to implementation. Serious adverse event reports will be submitted as requested by the Sponsor and per IRB/HREC policies and regulations.

The potential participant must sign the consent form that is currently approved by the study site's IRB/HREC. Failure to provide informed consent renders the participant ineligible for the study.

